### **STUDY SCHEDULE AND TREATMENT**

Since MOBILITY is a pragmatic study, we will collect the above information, when possible, and in conjunction with patients' clinical visits. We will allow for data collection approximately monthly for the first three months, followed by every three months thereafter, for a total duration of 24 months. However, these visits and timeline are just guidelines. Data will be collected through information acquired during clinical visits. There is no minimum number of visits required for patients to continue to participate in MOBILITY and have their data collected. However, sites should not schedule patient appointments exclusively to conduct study specific visits or procedures. Therefore, it is anticipated that **not all study visits or procedures will be completed for every patient. However, we will emphasize the importance of collecting Month 6 and 24 data since those are primary outcomes.** Labs tests that are recommended in the Schedule of Events are based upon standard clinical practice guidelines, but will not be required for continuation in the study.

Each site will have a copy of the MOBILITY Projected Visit Dates Spreadsheet (also found on the website: MOBILITYstudy.org). The site coordinator will enter the patient's baseline visit date where indicated, and the recommended visit schedules will auto-populate. However, once patients are randomized at baseline, MOBILITY is primarily an observational pragmatic study, therefore, data will be collected only at clinical appointments.

**Screening/Baseline Procedures:** At screening and following informed consent/assent and review of initial study criteria, we will obtain demographic and clinical information as follows:

Demographic and Clinical Characteristics: Site staff will record patients' date of birth, sex, type of insurance, contact information, and prior type and duration of psychiatric treatments. Patients will report current daily nicotine intake (packs/day) and whether they currently use other drugs (checking all that apply from a list of common drugs). Data on treatments and substance use will also be collected at six-

month intervals.

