Caregiver Strain Questionnaire (P)	X	X	X	X	X	X	X	X	X	X	X
Other recommended measures											
Vital Signs [blood pressure, heart rate] (C)	X	X	X	X	X	X	X	X	X	X	X
Other recommended laboratory measures: d,e thyroid, renal and liver panels, pregnancy test, CBC, and Vitamin B12 (C)	X				X						X
Suicidality, Patient Health Questionnaire (PHQ)-Item 9 (C)	X	X	X	X	X	X	X	X	X	X	X
Zucker Hillside Side Effects Form (C)	X				X						X
Total Time/Visit for Youth Questionsf (minutes)	15-20	5	5	5	15-20	5	7	5	7	5	15-20
Total Time/Visit for Caregiver Questionsf (minutes)	15-20	5	5	5	15-20	5	7	5	7	5	15-20

P= Caregiver; Y= Youth, C= Clinician. Kiddie-SADS-Present and Lifetime-PL 2013;

aKSADS will be performed at any time point after enrollment.

bBaseline fasting serum glucose is highly recommended, however, results within the past six months will be acceptable.

cItems from the PROMIS=Patient Reported Outcome Measurement Information System;

dAny labs completed within the past 6 months are acceptable except for pregnancy test;

At baseline a negative serum or urine pregnancy test is required in girls who have reached menarche prior to prescribing metformin.

eLabs are recommended, however these are not required to start or continue in the study.

fClinician and other assessments (e.g. labs, vitals) are part of a routine clinical visit and therefore, do not add time.

Our population will be  $\geq$ 85%ile BMI (weight of such 8- and 9 year-olds will likely be comparable to an average 10-year-old child); 2) MET has a favorable side effect profile; and 3) prior reports as well as the investigators' previous experiences with the safe and well-tolerated use of MET in patients  $\geq$ 8 years old. All patients will have a renal panel prior to starting MET to evaluate for renal impairment that would preclude use of MET.

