Participants randomized to treatment with MET will start at a recommended dose of 500 mg orally at night and slowly titrated in 2-week intervals to ensure that each patient achieves maximum insulin-sensitizing effects of the drug while minimizing the chance of side effects (see Table 1). We selected 50kg as the weight at which we felt comfortable increasing to a maximum total daily dose of 2000mg (1000mg twice daily). These youth will be at a low-end adult-comparable weight. We anticipate that most participants  $\geq$ 10 years old will be  $>50$ kg, which is the 95%ile for weight for 10-year-olds of both sexes. Children  $<50$ kg, likely those patients  $<10$  years, will have a reduced maximum daily dose of 1500mg. If

patients exhibit untoward gastrointestinal side effects while taking MET, clinicians will have the option to switch to an equivalent dose of the once-daily extended-release form of MET, which may alleviate side effects. If a patient does not tolerate a specific dose, the clinician will also have the option of reducing that dose by 500mg/day to a minimum recommended daily dose of 500mg twice daily. At Week 8, the dose for the <50kg group may be titrated to the maximum of 2000mg/day (1000mg twice daily) if tolerated and strategy, in general, MET will be at steady-state target levels well before key outcomes are assessed at Month 6. We will also recommend that MET be taken with food to minimize side effects. If a participant's BMI percentile <5% (=underweight) his/her treatment with MET will be discontinued. Although the risk of low vitamin B12 while taking MET is associated with age > 50 years and having type II diabetes, we will monitor B12 levels and a CBC throughout study participation.

Clinicians and patients must be willing to be randomized to either treatment arm. However, the clinician may choose to initiate or continue (for those on a subtherapeutic dose) metformin at their clinical discretion regardless of randomization following a recommended initial 3 month period of treatment. These patients' data will be considered in a different analytic group regardless of randomization.

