**Other potential risks:** To guard against frustration and fatigue, questions and surveys have been carefully chosen by patients, parents, and stakeholders. However, when necessary, assessments can be divided to decrease the frustration and fatigue. In addition, research staff will be hired based on their research experience and work with children and adolescents. Lastly, patients and their parent(s)/legal guardian(s) will be advised that they do not have to participate in the study and that their participation is voluntary and refusal to participate will not impact their clinical care in any way. Their alternative to study participation is to continue to receive standard clinical care. **Additional weight gain or metabolic abnormalities:** Patients in the study will be closely monitored for weight gain and metabolic abnormalities. Clinicians, parents, or patients can discontinue assigned study treatment at any point, but will still be monitored for up to 24 month. If a patient continues to have substantial weight gain ( $> 10\%$ ) in the LIFE group, a clinician might decide to add MET to the treatment if clinically indicated. Likewise, if the patient is randomized to the MET + LIFE group and continues to have substantial weight ( $> 10\%$ ) they will have the option to continue MET and/or add another treatment or switch the patient's treatment for BSD, whichever is clinically indicated. If a participant's BMI percentile 5% (= underweight) his/her treatment with MET will be discontinued.

Although the risk of low vitamin B12 while taking MET is associated with age  $> 50$  years and having type II diabetes, we will encourage clinicians to monitor B12 levels and a CBC throughout study participation. We will educate all study-related clinicians about this potential side effect of metformin and the very rare clinical manifestations of MET-related vitamin B12 deficiency (i.e., peripheral neuropathy and pernicious anemia).

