**b. Anticipated Benefit Justifies the Risk** - We believe the risks associated with study participation are minimal. Despite patients being randomized to LIFE + MET or LIFE alone, this is a pragmatic observational study and there are minimal study specific procedures associated with participation. Additionally, patients will remain in the study and data will be collected regardless of whether they switch treatment arms or miss visits, although all of this information will be recorded. Youth with BSD taking SGAs receive low rates of basic metabolic monitoring and even lower rates of intervention for being overweight or obese, even though weight gain is the side effect of SGAs that causes them the most concern and is a common reason for poor adherence. Participation may increase their likelihood of receiving state-of-the art monitoring and intervention/prevention for weight gain, obesity, and metabolic disorders. Potential benefits also include the chance to contribute to a scientific investigation which may benefit other patients like themselves in the future. The study will benefit society as a whole by potentially providing clinicians with a new means to optimize efficacy, minimize risk for adverse reactions, and ultimately achieve better quality of life for patients treated with SGAs. We may also gain a better understanding of MET's effects on anthropomorphic measurements as well as glucose and lipid metabolism, which may ultimately improve our ability to prevent and/or manage the longer-term effects of SGA. Overall, the risks associated with this study are minimal and subjects may receive direct benefit from participation. Therefore, in the opinion of the research team, including patient, parent, and other stakeholders, the benefits of this study outweigh the risks.

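### LIFE patients who are given metformin after month 6 have no scheduled side-effect form or renal, liver or B12 check until month 24

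*Combined protocol and SAP*

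**What the plan says.** **Late metformin is allowed.** The text following Table 2 lets clinicians initiate metformin at their discretion "regardless of randomization following a recommended initial 3 month period of treatment", and says the data of such patients will form a separate analytic group. Section G.a (other potential risks) covers the LIFE patient who gains more than 10%: "a clinician might decide to add MET to the treatment if clinically indicated". Section G.b keeps these patients in follow-up: "data will be collected regardless of whether they switch treatment arms or miss visits".

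**The schedule has one anchor.** Under Study Schedule and Treatment: "The site coordinator will enter the patient's baseline visit date where indicated, and the recommended visit schedules will auto-populate". No text restarts the schedule, or adds an item, when metformin starts later.

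**What is scheduled when (Table 2).**
- Zucker form: baseline, months 6 and 24.
- Recommended row with thyroid, renal and liver panels, pregnancy test, CBC and B12: baseline, months 6 and 24.
- Recommended metabolic labs (insulin, lipids, glucose, HbA1c): baseline, months 6, 12, 18 and 24.
- Vital signs and medication list: every visit. Other Outcome Measures also asks open-ended adverse event questions at every visit.

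Section G.a says data will be collected no more often than Table 2 recommends.

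**Checks before metformin.** The text following Table 2 says: "All patients will have a renal panel prior to starting MET to evaluate for renal impairment that would preclude use of MET". A Table 2 footnote says: "At baseline a negative serum or urine pregnancy test is required in girls who have reached menarche prior to prescribing metformin".

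**The concern.** The plan expects some LIFE patients to take metformin, but its structured safety assessments follow the calendar of the baseline visit and not the date of first exposure. A patient who starts after the month 6 visit has only one such assessment left, at month 24, and the cap in section G.a tells sites not to add another.

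The Zucker form matters because it grades intensity in five domains, gastrointestinal among them. Section G.a lists diarrhea, nausea and vomiting as the common metformin effects, and the background describes gastrointestinal symptoms in the investigators' own trial as transient. A first form a year or more after the start is a poor record of such effects. It also has no common time since first dose, so on-drug data from late starters are hard to set beside those of patients randomised to metformin.

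A second issue is that the documents do not say whether the checks meant to precede metformin apply when it is started after baseline.

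**Working it through.** **1. Time to the first scheduled on-drug assessment.** The plan gives no figure to reproduce; this is subtraction on the Table 2 time points. For a start at month t, with the Zucker form and the renal, liver, CBC and B12 row due at months 6 and 24:

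wait(t) = (smallest of {6, 24} that exceeds t) − t

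The same rule is applied to the metabolic labs {6, 12, 18, 24} and to the every-visit items {1, 2, 3, 6, 9, 12, 15, 18, 21, 24}.

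| Metformin start (month) | Zucker form and renal/liver/CBC/B12 | Metabolic labs | AE questions, vital signs |
|---|---|---|---|
| 0 (as randomised) | 6 − 0 = 6 | 6 | 1 |
| 3 | 6 − 3 = 3 | 3 | 3 |
| just after 6 | 24 − 6 = about 18 | about 6 | about 3 |
| 9 | 24 − 9 = 15 | 3 | 3 |
| 12 | 24 − 12 = 12 | 6 | 3 |
| 18 | 24 − 18 = 6 | 6 | 3 |
| 21 | 24 − 21 = 3 | 3 | 3 |

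Waits are in months. For starts after month 6, the wait exceeds the 6 months of a patient starting at baseline when 24 − t > 6, that is t < 18. The affected window is therefore a start after month 6 and before month 18. Any start after month 6 leaves one scheduled form.

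**2. Pregnancy test.** Four places, side by side:
- Laboratory Measures: required for girls past menarche who are randomised to metformin.
- Screening/Baseline Procedures: the only mandatory screening test, for girls past menarche.
- Table 2 footnote: required at baseline, before metformin is prescribed.
- Table 2 row: recommended at baseline, months 6 and 24.

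None requires a test when metformin starts later. For a girl past menarche at baseline who starts at month 12, the required test is 12 months old and the last recommended one is 12 − 6 = 6 months old. Footnote d accepts other labs from the past 6 months but excludes the pregnancy test.

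**3. Renal panel.** The statement after Table 2 that all patients will have one before metformin does not agree with three other places. Screening/Baseline Procedures continues to follow patients without baseline labs. Footnote e says labs are not required to start or continue. The text under Exclusion Criteria does not exclude patients who cannot obtain a creatinine. Table 2 has no column tied to a later start.

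**The case against.** The strongest reply is that safety observation does not stop after a late start. Adverse event questions are asked at every visit, the Data and Safety Monitoring plan has event reports collected systematically at visits and reviewed by the safety board twice a year, vital signs are taken each time, and metabolic labs recur every 6 months. Clinicians are to be taught to obtain labs before initiating metformin and encouraged to monitor B12 and CBC throughout. This stands: a reader might infer that harms in late starters would go unseen, and the documents do not support that. What is missing is the graded form and scheduled time points for the renal, liver and B12 tests. Open-ended questions do not replace the first, and monitoring throughout participation carries no dates beyond Table 2.

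The metformin arm has the same 18-month interval between months 6 and 24. True, but a patient who starts as randomised reaches it after one on-drug assessment; a late starter may have had none.

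Three other inferences also go too far:
- *Late starters' events will be counted as LIFE harms.* The text following Table 2 puts these patients in a separate analytic group. It does not say how their adverse events will be tabulated, so the fair complaint is that this is unspecified.
- *A girl who reaches menarche after baseline would have no test.* Table 2 recommends one at months 6 and 24. What is absent is a requirement at the later start.
- *Every late starter is affected.* Starts between months 3 and 6, or from month 18 on, wait no more than 6 months.

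The labs are recommendations and Table 2 calls its timing approximate, so actual gaps may be shorter or longer. The Zucker form is not a lab, however, and the cap on frequency discourages adding it.

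**Conclusion.** The point holds as a gap in structured assessment. For a metformin start after month 6 and before month 18, the first scheduled Zucker form and renal, liver, CBC and B12 row come more than 6 and up to about 18 months later, against 6 months for a patient starting at baseline. The 18 months is a maximum, reached only by a start just after the month 6 visit. These figures assume that visits follow Table 2 and that sites observe the frequency cap.

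The documents give no expected rate of late metformin starts in the LIFE arm, so the number of patients concerned cannot be derived and none is given here.

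Separately, the passages on the renal panel contradict each other, and those on the pregnancy test leave a later start unaddressed. Both need reconciling whatever view is taken of the interval. The point does not affect the analysis of BMI z-score; it concerns how well on-drug harms are recorded and compared. It is worth correcting because the correction is cheap.

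**What to change.** 1. Record the date of first metformin prescription for every participant, whatever the arm, and carry it in the visit-date spreadsheet beside the baseline date. The medication list already collected at each visit supplies most of this.
2. For anyone who starts metformin after baseline, add the Zucker form at existing clinical visits after the start, including one about 6 months after it where follow-up allows (starts up to month 18, since 18 + 6 = 24). Add a matching exception to the frequency cap in section G.a.
3. Give the safety board adverse event counts by randomised arm and by whether the patient was taking metformin at onset, and state how this relates to the separate analytic group described after Table 2.
4. Reconcile Laboratory Measures, Screening/Baseline Procedures, Table 2 with its footnotes and following text, and Exclusion Criteria. They should say whether the pregnancy test and labs before metformin, and the recommended labs during it, apply when it is started after baseline. Which rule should apply is for the investigators; none is proposed here.

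The cost is one date field, a footnote and a few extra clinician-completed forms at visits that take place anyway. Table 2 itself treats clinician assessments as adding no visit time.

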#### **A. SPECIFIC AIMS**

The specific aim of this study is to address the significant gap in the evidence base for metformin (MET) use in overweight and obese youth with Bipolar Spectrum Disorders (BSD).

The overall objective of this prospective, large, PRAGMATIC randomized trial is to study the impact of MET and healthy lifestyle intervention (LIFE) vs. LIFE alone on patient-centered outcomes of body weight, Second Generation Antipsychotics (SGA) adherence and satisfaction, psychiatric symptom burden (e.g. mood/anxiety), and quality of life (QoL). We will also examine metabolic outcomes.

**Specific Aim 1:** Assess the overall and subgroup-specific impact of MET+LIFE versus LIFE alone on short- (6mo) and long-term (24mo) **weight and metabolic health** in overweight and obese youth with BSD.

**H1.1:** Overall, assignment to treatment with MET will abrogate more weight gain and lead to fewer adverse metabolic outcomes than LIFE alone at 6 and 24 months.

**H1.2:** (Heterogeneity of Treatment Effects [HTE]): MET's effectiveness at abrogating weight gain and components of metabolic syndrome will vary with respect to the following factors (see Patient Population and Background for rationale and prior data): 1) Change in BMI z-score from SGA initiation to baseline (in patients already receiving SGA treatment); 2) Prior exposure to and duration of SGA treatment; 3) Baseline BMI z- score; 4) Baseline psychotropic weight burden (in SGA non-naïve patients; as defined in Measures below); 5) BSD as diagnosed by a structured interview; 6) Age; 7) Type of insurance (public/private); 8) Ethnicity (Hispanic/Non); 9) Baseline insulin resistance (HOMA-IR); 10) Race (African-American (AA) vs non-AA).

**Specific Aim 2:** Assess the overall and subgroup-specific impact of MET+LIFE vs. LIFE alone on short- (6mo) and long-term (24mo) **SGA adherence and treatment satisfaction**, including assessment of how these effects may be mediated by MET effects on weight gain.

**H2.1:** Overall, assignment to treatment with MET will lead to better SGA adherence and greater treatment satisfaction than LIFE alone after both 6 and 24 months.

**H2.2:** (HTE): MET effectiveness with regard to SGA adherence will vary with respect to: 1) Baseline weight acceptability; 2) Baseline psychotropic medication treatment acceptability; 3) Type of insurance (public/private).

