**Figure 1: MET prevention and intervention effects SGA-induced weight gain in youth**  
**Group1=SGA-non-naïve Group 2= SGA-naïve**

This group difference resulted in part from the immediate decrease in BMI z score in the SGA naïve group (BMI z score decreased by 0.23). BMI z score of the SGA non- naïve group decreased by 0.27+0.5 during the 6 months on MET. SGA naïve patients responded at lower MET doses than SGA non-naïve patients ( $764 \pm 225$  mg/d vs.  $834 \pm 285$ ). Additional determinates of MET response were: 1) Higher baseline BMI z score ( $p<0.0001$ ); 2) Longer length of SGA treatment prior to MET initiation ( $p=0.049$ ); and, 3) A  $> 7\%$  increase in weight over the 2 months prior to starting MET ( $p=0.0007$ ). These data confirm our previous results that MET abrogates SGA-induced abnormal weight gain in youth and also adds concerning information that a larger proportion of youth on SGAs are affected by weight gain than previously reported.

**IMPACT Study:** Most recently, [name] completed a large rigorously controlled NIMH-supported study of youth with psychiatric disorders and  $\text{BMI} > 85\%$ ile and SGA-related weight gain. Participants were randomized to 1 of 3 arms: 1) continuation of current SGA (control arm) ( $N=44$ ); 2) switch from current SGA to lower-risk agent (LRA) ( $N=30$ ) or 3) co-treatment with MET + continuation of current SGA (MET) ( $N=46$ ).

Sample characteristics were as follows: Age: 13.7 (7.6-19.9;  $<18=88\%$ ) Male=65% Hispanic:12% Black: 28%. At 12 and 24 weeks there was a significant decrease in BMI Z-scores in the MET (-0.034, -0.088, respectively) and LRA (-0.051, -0.112) groups compared with the control group (+0.026, +0.040). Additionally, at 24 months weight gain in the control group was 8.5lbs and 0.3lbs in the LRA group. In contrast, the MET group had an average decrease of -0.4lbs. 14.9% in the MET lost  $>5\%$  of weight compared to 2.3% in the control group and 10.0% in the LRA group (Fisher's exact,  $p=0.059$ ). Importantly, dropout rates in the LRA (39%) and control (28%) groups were higher than in the MET (24%) group. The most common (58%) reason for discontinuation in the LRA group was "inadequate therapeutic effect."

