The basic model for outcomes will be a GLMM with change from baseline to either 6- or 24- months as the dependent variable. Independent variables will include fixed-effect terms for randomized treatment group (MET), baseline value of the outcome, and random site effects. For HTE analyses, a baseline value-by-MET interaction (to assess HTE due to baseline status) will be included, and for particular domains additional continuous or categorical covariates and treatment-by-covariate interaction terms will be added to assess HTE. Outcomes within each domain will share the same set of HTE terms, specified in the Specific Aims. Because the subgroups are in general correlated (e.g., duration of SGA treatment, weight gain history and psychotropic weight burden will be correlated with baseline BMI), we will include multiple first-order HTE terms simultaneously (to assess heterogeneity independently attributable to each moderator), but will also fit separate models for each term to gauge the impact of this correlation on our conclusions. Higher-order treatment-by-covariate interactions will not be included a priori, but will be explored with rigorous adjustment for multiple testing, using step-down testing (removing highest-order interaction terms first) or information criteria based on penalized likelihoods to guide model selection.

**Marginal Structural Modeling for Causal Inference:** SA1 concerns the overall and sub-group specific effects of MET on abrogation of weight gain (with changes in BMI z-score from baseline as outcomes) and metabolic health, particularly metabolic syndrome and its component criteria. BMI and adherence measures are obtained at all study visits, so our models for these measures will use all available observations by treating the longitudinal series of changes in these variables and SGA treatment as dynamically dependent on each other. We will use marginal structural models to address this bi-directional dependence, computing the probability of SGA treatment regimen change at each visit within weight gain treatment regimen groups and using appropriately normalized versions of the inverse of the probability as the stabilized weights.

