Exacerbation of BSD is also a risk, however patients will be treated for BSD as clinical indicated and there are no restrictions on psychotropic medications use. Patients will be monitored closely by site clinicians who will use the YMRS to systematically assess manic symptoms and the PHQ-9 item #9, to assess current suicidality. Patients will remain in the study even if they require a change in treatment or psychiatric hospitalization. These events will be recorded as psychiatric symptom burden outcomes. Patients who become pregnant during their study participation will continue to be followed. We will encourage treating clinicians to discontinue metformin if it is being prescribed for study participation and to consult with the prescribing clinician prior to discontinuation, if it is prescribed by another clinician and for reasons unrelated to the study.

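### The marginal structural model weights only SGA changes, while off-assignment metformin has no weight and is sent to an undefined analytic group, so the Aim 1 BMI z-score effect is not tied to assignment

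*Combined protocol and SAP*

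**What the plan says.** H1.1 (Section A) is about assignment: "Overall, assignment to treatment with MET will abrogate more weight gain" than LIFE alone, at 6 and 24 months. In Section E.b the basic model is a mixed model with randomised group, baseline value and random site effects; no weights are mentioned. The next paragraph, on marginal structural modelling, says that the models for BMI and adherence use all visits and treat weight and SGA treatment as mutually dependent. It builds stabilised weights by "computing the probability of SGA treatment regimen change at each visit within weight gain treatment regimen groups".

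Three places govern treatment changes after randomisation:

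- Section G.a (Other potential risks), after a gain of more than 10%: "in the LIFE group, a clinician might decide to add MET to the treatment if clinically indicated". For MET + LIFE, "they will have the option to continue MET and/or add another treatment or switch the patient's treatment for BSD, whichever is clinically indicated".
- Section G.a (exacerbation of BSD): "there are no restrictions on psychotropic medications use", with no distinction by arm.
- The metformin text after Table 2: following a recommended first three months, "the clinician may choose to initiate or continue (for those on a subtherapeutic dose) metformin at their clinical discretion regardless of randomization". Then: "These patients' data will be considered in a different analytic group regardless of randomization".

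The medication list is collected at every visit (Table 2). Section G.b says that follow-up continues, and is recorded, when a patient changes arm.

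**The concern.** The plan recognises that a patient's weight history drives treatment and that treatment drives weight, and chooses marginal structural models for that reason. It then models only one of the outcome-driven changes that it allows. A LIFE patient who starts metformin after gaining weight has been selected on the outcome itself, and nothing in the weights deals with that.

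The regrouping sentence makes this more serious. Moving clinician-started metformin patients out of their randomised group conflicts with the randomised-group term of the basic model and with H1.1. It also makes it plausible that the groups named in the weighting sentence mean treatment received. Read that way, the patients who gain most leave LIFE and join the metformin group. At stake is whether the main Aim 1 result estimates the effect of assignment, a defined effect of metformin, or a comparison distorted by who was given metformin.

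**Working it through.** The documents give no figure for this point, so there is none to reproduce. The text is compared first; the sizes are then illustrated under stated assumptions.

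**1. What may change, and what is weighted**

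| Change after randomisation | Where allowed | In the weights? |
|---|---|---|
| SGA regimen | Both arms | Yes |
| Metformin started | LIFE: after >10% gain, or at discretion after a recommended 3 months | No |
| Another treatment added | Listed for MET + LIFE after >10% gain | No |
| Assigned treatment stopped | Either arm, at any time (G.a) | No |

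**2. Effects taken from the documents.** Section C (IMPACT Study) reports 12- and 24-week changes in BMI z-score "in the MET (-0.034, -0.088, respectively) and LRA (-0.051, -0.112) groups compared with the control group (+0.026, +0.040"). At 24 weeks:

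- metformin minus control: -0.088 - 0.040 = -0.128
- SGA switch minus control: -0.112 - 0.040 = -0.152

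**3. Illustration A: effects as constant shifts held to month 24.** Assumptions: visits every 3 months; individual slopes with mean 0.02 and SD 0.06 z per 3 months; above a gain of 0.2 z, a probability of 0.4 per visit of metformin start (LIFE) or SGA switch (MET + LIFE); 3% background SGA switching. About 35% of LIFE then start metformin. Each weight is the product over visits of P(SGA status | arm) / P(SGA status | arm, BMI z history). Month-24 change is regressed on the listed terms.

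| Analysis | Estimate |
|---|---|
| Metformin effect without crossover (by construction) | -0.128 |
| Randomised arm, no weights | -0.113 |
| Randomised arm, SGA weights, no SGA term | -0.115 |
| Randomised arm, SGA weights, SGA term | -0.086 |
| Metformin received, SGA weights, SGA term | about +0.25 |
| LIFE metformin starters removed | about +0.1 |
| Metformin-start weight and term added | -0.128 to -0.135 |

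At about 15% crossover the treatment-received estimate is about +0.03. The sign turns because the LIFE patients with the steepest gain are counted as metformin patients. That raises the metformin mean and lowers the mean of those left in LIFE.

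**4. Illustration B: effects that build up linearly.** Metformin acts at -0.128/12 z per month, so the effect without crossover is -0.128 x 24/12 = -0.256 at month 24. Metformin can start in LIFE from month 3 above a gain of 0.25 z, with probability 0.05, 0.15 or 0.30 per visit. SGA switching is at the same rate in both arms.

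| LIFE starting metformin | As randomised, SGA weights | Own target: no SGA change, metformin allowed | LIFE starters removed | Metformin received (unweighted) |
|---|---|---|---|---|
| 8% | -0.249 | -0.249 | -0.221 | -0.178 |
| 20% | -0.238 | -0.237 | -0.159 | -0.075 |
| 30% | -0.225 | -0.225 | -0.093 | +0.015 |

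With patients kept as randomised, the SGA weights recover their own target. They fall short of the no-crossover effect by 0.256 - 0.249 = 0.007, 0.256 - 0.238 = 0.018 and 0.256 - 0.225 = 0.031, or 3%, 7% and 12%. At 20% crossover, removal loses 1 - 0.159/0.256 = 38% of the effect, and grouping by treatment received loses 1 - 0.075/0.256 = 71%.

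**5. Cost of keeping patients as randomised.** If a share c of LIFE gets the full metformin effect, the contrast is 0.128 x (1 - c), and power is about Phi(contrast / (SD x sqrt(2/n)) - 1.96). Take SD 0.5, read from the pilot in Section C. For c = 30% the contrast is 0.0896. Power is 96.7% with 900 per arm and 95.0% with 810 per arm (90% retention). For c = 50% it is 77.5% and 73.1%.

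**The case against.** A reader might infer something stronger: that the plan corrects for rescue in the MET arm but not in LIFE, so the metformin effect is biased as specified. The documents do not support that, for four reasons.

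- SGA changes are unrestricted in both arms and are weighted in both, and the other treatment that may be added in MET + LIFE has no weight either. In Illustration A the gap between the SGA-weighted estimate and the assignment effect comes from letting only MET + LIFE switch SGA in response to gain. If LIFE gainers also switch with probability 0.2 per visit, the two are -0.085 and -0.087. With 0.4 the order reverses (-0.086 and -0.073).
- With patients as randomised, the SGA-only weights are consistent for the effect with no SGA change and metformin allowed (Illustration B). The shortfall against -0.128 or -0.256 is a comparison with a different target.
- Section E.b does not say that SGA regimen is a term in the outcome model. Without it, the weighted estimate agrees with the assignment effect (-0.115 against -0.113).
- The basic model by randomised group is unweighted and untouched by the missing weight. Crossover dilutes it but does not bias it for assignment.

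The sizes are also soft. Rescue probabilities, triggers and slopes are not in the documents. The -0.152 comes from a randomised switch to a lower-risk agent, and Section B itself calls the weight benefit of switching limited or inconsistent.

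All of this stands. It does not settle which of the two models answers H1.1, what the groups in the weighting sentence are, or what the separate analytic group is for. The treatment-received and removal results do not depend on arm-specific switching.

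**Conclusion.** The concern holds in a conditional form. Off-assignment metformin is outcome-driven and unweighted, as is other treatment added in MET + LIFE, and the regrouping rule after Table 2 contradicts both the randomised-group term and H1.1.

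If the groups mean treatment received, the metformin effect is confounded by indication. Illustration A gives about +0.03 to +0.25 against -0.128 at 15% to 35% crossover. Illustration B is milder: -0.178 to +0.015 against -0.256 at 8% to 30%. Removing LIFE starters also pulls the estimate towards zero, or past it in Illustration A. If patients stay as randomised, nothing is biased for the SGA-weighted target, but that target is neither the effect of assignment nor the effect of metformin without crossover, and the plan does not say that it is wanted.

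The text does not prove that an analysis by treatment received is intended, so a wrong-sign result is a risk of one reading and not a prediction. All sizes rest on assumed crossover and on carrying 24-week effects to month 24.

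**What to change.** 1. Reconcile the regrouping sentence after Table 2 with Section E.b. State that the H1.1 analysis keeps every patient in the randomised arm whatever is started or stopped later, and uses neither SGA-change nor metformin weights. Define the groups in the weighting sentence.
2. If the effect of metformin without crossover is wanted, make it a separately labelled supplementary analysis. At each visit, also model the probability of starting or stopping metformin, and of other added weight treatments, given arm, BMI z history, SGA regimen and adherence. Multiply the stabilised weights, truncate them, and include open-label metformin in the outcome model.

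The medication list at each visit supplies the treatment data, so no new collection is needed. The cost is SAP wording, further weight modelling and a somewhat wider interval for the supplementary estimate; in a run of Illustration A the largest weight rose from about 13 to about 21. No clinical rule on adding, switching or stopping treatment changes.
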